5.3.2. Titration Schedule and Dose Adjustments

Subjects randomized to the topiramate arm will start 25mg topiramate once daily in the evening. On day 4 following randomization a morning dose of 25 mg will be added. On day 8 following randomization an additional 25 mg tablet will be added in the evening, and on day 12 a second morning dose will be added so that the subject will be taking a total of 50mg twice daily. Subjects who experience an adverse event during the dose titration may continue at the highest tolerated dose for one week prior to an additional attempt to increase to the targeted dose. Those who are tolerant of a lower dose but intolerant of the target dose will continue on the highest tolerated dose. Results will be analyzed in an intent to treat fashion. If a subject develops a treatment related adverse event, the dose may be lowered at the discretion of the site PI in order to establish a lower maximally tolerated dose. Those who have an adverse event and are unable to continue medication will undergo a termination visit.

In accordance with local regulatory requirements, the investigator, designated site staff, or head of the medical institution (where applicable) must document the amount of investigational product dispensed and/or administered to study subjects, the amount received from the central pharmacy, and the amount destroyed upon completion of the study. An investigator is responsible for ensuring product accountability records are maintained throughout the course of the study. The inventory will include details of *topiramate* received and dispensed to subjects, batch, and ID numbers. All unused *capsules* must be kept until reconciliation of delivery records with accountability logs by the monitor. After the monitor has performed accountability, the site will be instructed by the DCC or designee to either destroy the remaining study drug or return it to the

Central Pharmacy or manufacturer. An accounting must be made of any drug deliberately or accidentally destroyed. Discrepancies between the amount of topiramate received and dispensed drug must be reconciled.

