6.13. Early Termination and Premature Withdrawal

Subjects have the right to withdraw from the study at any time without prejudice. The site Investigator may withdraw study drug from a subject in the study in the event of intercurrent illness, adverse events, other reasons concerning the health or well-being of the subject or other administrative reasons. Early termination will be implemented in the case of emergency disclosure of drug treatment (i.e., unblinding). **NOTE: All efforts should be made by study staff to encourage subjects to return for follow-up visit(s). If a subject withdraws consent from the study in writing, no further contact can be made.**

A subject may discontinue study medication for the following reasons:

Administrative

1. Withdrawal of consent
2. Request of Sponsor or Principal Investigator
3. Request of primary care physician
4. Pregnancy
5. Subject deemed lost to follow up/failure to return
6. Termination of study
7. Other

Adverse Event

1. Worsening of the disease under study
2. Worsening of pre-existing disease (other than disease under study)
3. Intercurrent illness
4. Death
5. Major/clinically significant alteration in laboratory values after beginning study drug
6. Suicidality based on the C-SSRS
7. Other adverse event

In the event a participant discontinues study medication for any reason, every effort should be made to complete the evaluation visits at week 32, 64, and 96. An early termination visit should be completed for all participants who are unable or unwilling to complete additional evaluation visits. If a subject is unable to return to the site, or refuses to complete all termination visit procedures, any reasonable study procedures to which the subject consents will be completed.

Should a scheduled in-person visit be impossible, conduct as many of the verbal assessments as possible, with special emphasis on obtaining information on possible AEs, and arrange for return of study drug. Every effort will be made to determine the subject's health status at withdrawal.

Reasons for early termination of the subject prior to completion of the study must be stated in the CRF and in the site source documentation for all study subjects who were enrolled in the study. The CCC and the IMM must be informed within 24 hours of all study subjects who are withdrawn due to an adverse event.

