6.13.4. On Study/Off-Intervention Evaluations

Every possible effort should be made by the site PI to encourage subjects who are no longer taking study drug to remain in the study. They should explain that continued participation will teach us more about the natural history of CSPN progression, the impact of metabolic improvement and weight loss on CSPN, and the clinical relevance of IENFD and other surrogate measures of CSPN progression.

When subjects decide to go off the study drug, it will be a reportable event and the project manager will discuss the reasons for this with site staff to learn the specifics in each case and provide advice on an individual basis about the best ways to keep the subject engaged in the

project. These subjects and their physicians will not be told whether they were given topiramate or placebo.

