6.14. Off-Study Requirements

Adverse events will be followed up to 30 days after study completion (including early termination) or until the site Principal Investigator deems the condition to have resolved or the condition has stabilized (whichever occurs first).

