7.1.14.1. Distal Thigh Skin Biopsy

A distal thigh skin biopsy is collected at the following visits: Baseline (Visit 02), Week 32 (Visit 04), Week 64 (Visit 06), and Week 96 (Visit 08/Termination) and/or Early Termination.

A 3mm punch biopsy will be taken from the distal, lateral thigh 10 cm distal to superior margin of the patella.

Refer to the *Reference Manual for skin punch biopsy*.

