10.2. Data Monitoring

All aspects of the study will be monitored by qualified individuals designated by the sponsor. Monitoring will be conducted according to Good Clinical Practice and applicable government regulations. The investigator agrees to allow monitors access to the clinical supplies, dispensing and storage areas, and to the clinical files of the study subjects, and, if requested, agrees to assist the monitors.

Safety monitoring will include careful assessment and appropriate reporting of adverse events. Medical monitoring will include contemporaneous assessment of serious adverse events.

The monitoring of subject safety and data quality will follow the NINDS Guidelines for Data and Safety Monitoring in Clinical Trials. A Data and Safety Monitoring Board (DSMB) appointed by the NIH/NINDS will meet at 24-week intervals (or as determined by the NINDS) to review partially unblinded study data provided by the study statistician. This committee will monitor rates of adverse events and endpoints in the trial and will monitor the performance of the trial. The frequency and format of DSMB meetings, reports, and guidelines for interim analysis will be agreed upon prior to study subject enrollment.

The Protocol PI will appoint an Independent Medical Monitor (IMM) to review all adverse events, in a blinded fashion, on a periodic basis. In addition, the IMM will review all events that meet the regulatory definition of a Serious Adverse Event, upon receipt of notification via the Electronic Data Capture (EDC) system.

An adverse event (AE) is any unfavorable and unintended sign (including a clinically significant abnormal laboratory finding, for example), symptom, or disease temporally associated with a study, use of a drug product or device whether or not considered related to the drug product or device. The FDA, Office of Human Research Protection (OHRP), and NeuroNEXT CIRB requirements for reporting AEs will be followed. Subjects will be monitored for AEs from the time they sign consent until 30 days following permanent discontinuation of study drug. Adverse events during the screening phase (from the time the subject signs consent until they are randomized) shall only include events related to study procedures, i.e. infection of skin biopsy site.

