At that point, all ongoing AEs will be followed to resolution, but no new AEs will be recorded. The IMM/DSMB will review cumulative AEs; the frequency of this review will be determined by the IMM/DSMB in conjunction with the Protocol PI.

Each Clinical Study Site Investigator and research team (co-Investigators, research nurse, clinical trial coordinator) are responsible for identifying and reporting AEs and determining the relationship of the event to the study drug/study procedures. Aggregate reports blinded by treatment group, detailed by severity, attribution (expected or unexpected), and relationship to the study drug/study procedures, will be available from the DCC for review by the IMM. A separate report detailing protocol compliance will also be available monthly from the DCC for review by the Protocol PI, who will provide feedback to individual sites as needed. The Protocol Steering Committee (PSC) will advise the Protocol PI as to whether the protocol or informed consent document requires revision based on these reports.

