11.4.2. Assessment and Recording of Adverse Events

This study will utilize the CTCAE version 4.0 coding system for adverse event recording. Adverse events reported using CTCAE will be recoded into MedDRA terms by the DCC.

Assessment of Adverse Events

At each visit (including telephone interviews), the subject will be asked "Have you had any problems or symptoms since your last visit?" in order to determine the occurrence of adverse events. If the subject reports an adverse event, the Investigator will determine:

1. Type of event
2. Date of onset and resolution (duration)
3. Severity (mild, moderate, severe)
4. Seriousness (does the event meet the above definition for an SAE)
5. Causality, relation to investigational product and disease
6. Action taken regarding investigational product
7. Outcome

Relatedness of Adverse Event to Investigational Product

The relationship of the AE to the investigational product should be specified by the Site Investigator, using the following definitions:

1. Not Related: Concomitant illness, accident or event with no reasonable association with treatment.
2. Unlikely: The reaction has little or no temporal sequence from administration of the investigational product, and/or a more likely alternative etiology exists.
3. Possibly Related: The reaction follows a reasonably temporal sequence from administration of the investigational product and follows a known response pattern to the suspected investigational product; the reaction could have been produced by the investigational product or could have been produced by the subject's clinical state or by other modes of therapy administered to the subject. (suspected ADR)
4. Probably Related: The reaction follows a reasonably temporal sequence from administration of investigational product; is confirmed by discontinuation of the investigational product or by re-challenge; and cannot be reasonably explained by the known characteristics of the subject's clinical state. (suspected ADR)
5. Definitely Related: The reaction follows a reasonable temporal sequence from administration of investigational product; that follows a known or expected response pattern to the investigational product; and that is confirmed by improvement on stopping or reducing the dosage of the investigational product, and reappearance of the reaction on repeated exposure. (suspected ADR)

Recording of Adverse Events

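### Recording of new adverse events closes 30 days after permanent drug discontinuation, but off-drug participants stay on study, with biopsies and AE review, to week 96; the two rules conflict

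*Combined protocol and SAP*

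**What the plan says.** **Recording window.** Section 10.2 states: "Subjects will be monitored for AEs from the time they sign consent until 30 days following permanent discontinuation of study drug". Section 11.4.1.1 repeats that sentence. Section 10.2 then adds: "At that point, all ongoing AEs will be followed to resolution, but no new AEs will be recorded". The sentence just before this one concerns screening, but the only sensible referent for the cut-off is the end of the 30-day window.

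**Off-drug participants stay.** Section 6.13 says that after study medication is stopped for any reason, "every effort should be made to complete the evaluation visits at week 32, 64, and 96". Section 6.13.4 asks the site investigator to "encourage subjects who are no longer taking study drug to remain in the study". Section 7.1.14.1 places a distal thigh punch biopsy at baseline, at those three evaluation visits, and/or at early termination.

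**AE review is tied to visits.** Section 11.4.2 says: "At each visit (including telephone interviews), the subject will be asked" about new problems or symptoms. The visit lists in sections 6.5 to 6.12 and the table in Appendix A mark AE review at every visit. None exempts participants who are off drug.

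**Related text.**
- Section 6.14 uses another anchor: "Adverse events will be followed up to 30 days after study completion (including early termination"), or until the event resolves or stabilises, whichever is first.
- Section 5.3.2 says: "Those who have an adverse event and are unable to continue medication will undergo a termination visit". Section 6.13 keeps the early termination visit for those unable or unwilling to complete further evaluation visits.
- Sections 3 and 6.11 set the final safety contact at 4 weeks ± 7 days after the last dose.

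**The concern.** The AE window is anchored to the drug, while participation and study procedures are anchored to week 96. Between the two lies a period in which a participant attends visits, has biopsies and is asked about AEs, but under section 10.2 no new event is to be recorded.

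Three things are at stake:

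- **Procedure risk.** Sections 10.2 and 11.4.1.1 treat biopsy-site infection as recordable even during screening. The same infection after a week 64 biopsy in someone long off drug falls outside the window.
- **Consistency across sites.** Section 4.4 plans 15 sites. One site could log an event raised at week 64 on the strength of section 11.4.2, and another could decline to log it on the strength of section 10.2. Both would be following the protocol.
- **Comparison of arms.** Section 10.2 has the DSMB monitor AE rates. If permanent discontinuation differs by arm, so does the observed AE time. Events that were never recorded cannot be reliably recovered later.

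**Working it through.** **1. The passages side by side, for a participant permanently off drug for more than 30 days**

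| Question | Answer | Section |
|---|---|---|
| Still on study? | Yes, if willing | 6.13, 6.13.4 |
| Still biopsied? | Yes, at each remaining evaluation visit | 7.1.14.1 |
| Asked about AEs? | Yes, at every visit and call | 6.5 to 6.12, 11.4.2, Appendix A |
| Serious events reported? | All, within 24 hours; no link to the window | 11.4.2 |
| New AE recorded? | No | 10.2; window repeated in 11.4.1.1 |

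The last row cannot be squared with the two above it.

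**2. Length of the gap for one participant**

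Inputs: a 30-day tail (30/7 = 4.3 weeks) from section 10.2; end of follow-up at week 96; biopsies at weeks 32, 64 and 96. For permanent stopping at week t:

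- the window closes at t + 4.3
- uncovered weeks = 96 − t − 30/7

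| Stops at week | Window closes at week | Uncovered weeks | Biopsies after closure |
|---|---|---|---|
| 16 | 20.3 | 75.7 | 32, 64, 96 |
| 32 | 36.3 | 59.7 | 64, 96 |
| 64 | 68.3 | 27.7 | 96 |
| 80 | 84.3 | 11.7 | 96 |

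**3. Could the loss differ by arm?**

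The plan gives no figure to reproduce here. The nearest is dropout of 4%, 8% and 12%: 125 × 0.96 = 120, 125 × 0.92 = 115 and 125 × 0.88 = 110, which matches the visit table in section 3. That is pooled study dropout, not drug discontinuation by arm, so the rates below are assumptions. Every stop is taken as permanent and every stopper as staying to week 96.

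Share of on-study time lost = d × (mean uncovered weeks) / 96, where d is the proportion stopping.

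- Stops spread evenly over 96 weeks: mean uncovered = (96 − 4.286)² / (2 × 96) = 43.8 weeks.
- Stops spread evenly over the first 16 weeks: mean uncovered = 96 − 8 − 4.286 = 83.7 weeks.

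| Stopping, placebo vs topiramate (assumed) | Lost, stops spread over 96 weeks | Lost, stops in first 16 weeks |
|---|---|---|
| 10% vs 10% | 4.6% vs 4.6% | 8.7% vs 8.7% |
| 10% vs 20% | 4.6% vs 9.1% | 8.7% vs 17.4% |
| 10% vs 30% | 4.6% vs 13.7% | 8.7% vs 26.2% |
| 15% vs 40% | 6.8% vs 18.3% | 13.1% vs 34.9% |

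The imbalance runs from 0 to about 22 percentage points (34.9 − 13.1 = 21.8). It depends wholly on rates that the documents do not give. Because some stoppers will restart or leave, each figure is an upper bound for its assumed rates.

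**4. Final safety contact**

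4 weeks ± 7 days is day 21 to day 35. The contact can therefore fall up to 30 − 21 = 9 days before the window closes. For an early stopper who stays, it also comes before the later biopsies.

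**The case against.** **Recording may not stop in practice.** AE review is scheduled throughout, section 11.4 stresses reporting all AEs, and section 11.4.2 requires every serious event within 24 hours. This is a fair point. The documents do not settle which rule would prevail, so the finding is a contradiction with a consequence if section 10.2 is followed, not proof that data will be missing. Scheduled questions do not cure it, because a site can ask and still not log the answer.

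**A drug-anchored window can be deliberate.** A 30-day tail is a reasonable on-treatment definition. That stands, but a flag delivers the same on-treatment summary without discarding the rest.

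**The affected group may be small.** Section 5.3.2 may take participants who stop for an AE off study. Sections 5.3.2 and 8 provide for dose reduction, section 6.13.1 encourages restarting, and the clock starts only at permanent discontinuation. This stands and limits any estimate of size.

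**Section 6.14 may not conflict.** It can be read as follow-up of existing events only, which section 10.2 also provides for. That reading is tenable, so section 6.14 needs aligning but is not the main evidence.

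**Stronger readings the documents do not support.** A reader might infer that safety data will be cut short unequally between arms. That needs discontinuation to differ by arm in rate or timing. Section 8 makes this plausible, since its stopping rules for low bicarbonate, visual field defects and glaucoma symptoms target effects it describes for topiramate. But no rate by arm is given, and equal rates and timing give zero imbalance. A reader might also infer bias toward no difference. That holds only for events that the drug raises and that appear more than 30 days after stopping. Lost background events would instead make the arm with more stopping look falsely safer, and drug-caused events that occur on drug are largely kept.

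**Conclusion.** The contradiction is established from the text. Sections 10.2 and 11.4.1.1 tie the AE window to the drug, while sections 6.13, 6.13.4, 7.1.14.1 and 11.4.2 and Appendix A tie participation, biopsies and AE review to the visit schedule. If section 10.2 is applied as written, new events in on-study, off-drug participants go unrecorded, serious events and biopsy complications among them. The gap is about 76 weeks for a stop at week 16 and about 12 weeks for a stop at week 80, given follow-up to week 96.

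Unequal loss between arms is a conditional risk. Its size cannot be stated from the documents, and its direction varies with the type of event. The efficacy analyses, the sample size and the Go/No-Go rule are not touched. It is worth correcting because the fix is cheap and the lost data could not be reliably rebuilt.

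**What to change.** 1. Amend sections 10.2 and 11.4.1.1 so that new AEs are recorded from consent until 30 days after the last dose or the last study procedure, whichever is later. Remove or reword the sentence in section 10.2 that ends recording.
2. Add an on-drug/off-drug flag to the AE form, with on-drug running through 30 days after the last dose. Report both an on-treatment and a full on-study AE summary by arm, with exposure-adjusted rates.
3. Align section 6.14 with the same window, and say whether it covers new events or only follow-up of existing ones.
4. Reconcile the timing of the final safety contact in sections 3 and 6.11 with the 30-day window.
5. Reconcile sections 5.3.2 and 6.13 on whether participants who stop for an AE leave the study, since this decides how many are affected.

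The cost is wording, one form field and slightly more AE data entry for off-drug participants. The visits, calls and AE questions are already scheduled.

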11. DATA COLLECTION, SITE MONITORING, AND ADVERSE EXPERIENCE REPORTING

11.1. Data Management

Site personnel will collect, transcribe, correct, and transmit the data onto source documents, CRFs, and other forms used to report, track and record clinical research data. The DCC will monitor clinical sites to ensure compliance with data management requirements and Good Clinical Practices. The DCC is responsible for developing, testing, and managing clinical data management activities, as required, at the study sites, the CCC, and at the DCC.

The general NINDS Common Data Elements (CDE) will be used to construct data collection forms. All study data will be collected via systems created in collaboration with the DCC and will comply with all applicable guidelines regarding patient confidentiality and data integrity.

11.1.1. Registration

Registration of subjects on this protocol will employ an interactive data system in which the clinical study site will attest to the subject's eligibility as per protocol criteria and obtain appropriate informed consent. NeuroNEXT CIRB approval for the protocol must be on file at the DCC before accrual can occur from the clinical study site.

The DCC will use a system of coded identifiers to protect subject confidentiality. When the subject is registered to participate in the study using the DCC-provided web-based registration, the system will assign a subject ID number. The unique ID code will include a protocol ID, a site ID, and a unique subject ID. To confirm the correct subject ID, the data entry system will require a second entry of the unique subject ID and compare for consistency. In this fashion, no personal identifiers would be accessible to the DCC and the data will be collected on the correctly identified subject.

11.1.2. Data Entry

Data entry will occur at the enrolling clinical study sites. Data quality assurance and analyses will be performed by the DCC. The DCC, located at the University of Iowa, will coordinate all data and statistical services for the study, as well as on-site monitoring for all participating clinical study sites.

Data collection for this study will be accomplished with online electronic case report forms. Using encrypted communication links, online forms will be developed that contain the requisite data fields.

11.2. Role of Data Management

Data Management (DM) is the development, execution and supervision of plans, policies, programs, and practices that control, protect, deliver, and enhance the value of data and information assets.

All data will be managed in compliance with NeuroNEXT policies, and applicable Sponsor and regulatory requirements. The DCC will instruct site personnel to collect, transcribe, correct, and transmit the data onto source documents, CRFs, and other forms used to report, track and record clinical research data. The DCC will monitor clinical sites to ensure compliance with data management requirements and Good Clinical Practices. The DCC is responsible for developing, testing, and managing clinical data management activities, as required, at the clinical study sites (CSS), the CCC, and at the DCC.

The DCC is responsible for all aspects of clinical data management, and for properly instructing key study personnel (including the CCC, the CSS, and DCC staff) on how to collect, transcribe, correct and transmit the data onto CRFs or other data collection forms and logs.

The DCC is responsible for establishing procedures to ensure that clinical data management activities occur as required at the CCC, the CSS, and at the DCC.

